10 SUMMARY OF PROCEDURES

Visit (window)	Description	Screening	Baseline Evaluation (30 days from implant)	Implant Procedure (Day 0)	Post-stent placement assessment	Discharge or 3 days post- procedure ^a	1 Month Evaluation (30 days -7/+14 days)	6 Month Evaluation (180 ±30 days)	12 Month Evaluation (365 ±60 days)	24 and 36 Month Evaluation (±90 days)	48 and 60 Month Evaluation (±90 days)	Interval Evaluation ^b
Assessment of Inclusion and Exclusion Criteria	Medical records	Х	х	xc								
Informed Consent	IC		x ^d									
Assessment of baseline characteristics	H&P, labs, CEAP		х				Physical Exam Only	Physical Exam Only	Physical Exam Only			Physical Exam
Duplex Ultrasound	DUS					х		x ^e	х	Xi		х
Venogram	VG			Х	Х				x ^h			х
IVUS	IVUS			Х	Х				Х			Х
AE Assessment				Х	Х	Х	Х	Х	Х			Х
SAE Assessment										Xj	X ^j	
Anticoagulation Regimen				х		х	х	х	х			х
Pregnancy Test (women of child bearing years)			x ^f									
CIVIQ-2			Х					Х	Х			
VAS			х					х	х			
VCSS			х					Х	Х			
Biplane X-ray ^g									х			

a: Discharge or 3 days post-procedure, whichever comes first

b: Performed if patients present with symptoms of clinically significant obstruction of the target vessel. (See Section 9.10.)

c: Evaluate intra-procedural exclusion criteria prior to implant (See Section 8.2.3.)

d: Informed consent may be collected before or at the Baseline Evaluation visit.

e: Required only for the first 30 study patients to assess patency

f. Pregnancy test in females of child-bearing age must be collected within 48 hours of implant procedure

g: To assess stent integrity.

h: To assess primary patency

i: To assess patency

j: SAE Assessment may be performed via telephone.

STE-HUM-007P US Clinical Protocol Revision C

Confidential

Page 33 of 70

11 ADVERSE EVENTS

11.1 Event Definitions

11.1.1 Adverse Event

All Adverse Event (AE) data will be collected and recorded on the Adverse Event Form. At each evaluation, the Investigator or Investigator's designee will determine whether an AE has occurred.

An AE will be defined as any untoward medical occurrence in a subject that does not necessarily have a causal relationship with the investigational treatment. This will include any new undesirable experience (signs, symptoms, illness or other medical event), or worsening of a pre-existing condition. An AE may or may not be related to the medical (investigational) product.

If a pre-existing condition (any clinically significant abnormality) is present at the start of the study, it must be recorded as an adverse event if the frequency, intensity, or the character of the condition worsens during the Investigational Plan-defined surveillance.

Alterations in laboratory parameters will not be considered AEs unless such alteration is qualified as medical condition. For example, decrease in hemoglobin will not be considered an AE unless it meets the definition of anemia.

11.1.2 Serious Adverse Event

All **serious adverse events** (SAEs) must be reported immediately to the Sponsor or Sponsor Designee. For the purposes of this Investigational Plan, when an AE or complication meets the definition for a SAE as noted below, it will be considered as such and reported within **24 hours** of becoming aware of the event to the Sponsor or Sponsor's designee. These events may also need to be reported per requirements of the reviewing EC.

Serious Adverse Events are defined according ISO 14155 and are adverse events that:

- 1. Led to death
- 2. Led to a serious deterioration in the health of a patient that:
 - a. Resulted in a life-threatening illness or injury
 - b. Resulted in a permanent impairment of a body structure or a body function
 - c. Required in-patient hospitalization or prolonged hospitalization
 - d. Resulted in medical or surgical intervention to prevent permanent impairment to a body structure or a body function
- 3. Resulted in fetal distress, fetal death or a congenital abnormality or birth defect

STE-HUM-007P US Clinical Protocol Revision C

Confidential

Page 34 of 70

11.1.3 Device Deficiency

Device deficiency is inadequacy of a medical device related to its identity, quality, durability, reliability, safety or performance, such as malfunction, misuse or use error and inadequate labeling.

In addition to reporting qualifying event(s) (as described above) the study Investigator and Sponsor must each determine (in writing) whether device deficiency could have led to a serious adverse device effect (see definition below) if:

- a. suitable action had not been taken or
- b. intervention had not been made or
- c. if circumstances had been less fortunate.

11.1.4 Major Adverse Event (MAE)

All **major adverse events (MAEs)** must be reported within 24 hours of knowledge of the event to the Sponsor or Sponsor Designee. A subcategory of SAEs include any of the following primary safety endpoints occurring within 30 days of the study procedure:

- Device or procedure-related death
- Device or procedure-related bleeding at the target vessel and/or the target lesion or at the access site requiring surgical or endovascular intervention or blood transfusion ≥2 units
- Device or procedure-related arterial or venous injury occurring in the target vessel segment and/or target lesion location or at the access site requiring surgical or endovascular intervention
- Device or procedure related acute DVT outside of the target vein segment
- Clinically significant pulmonary embolism defined as being symptomatic with chest pain, hemoptysis, dyspnea, hypoxia etc... AND be documented on CT
- Embolization of stent

These events may also need to be reported per requirements of the reviewing EC.

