1 KEY PROTOCOL DEFINITIONS

PRE-PROCEDURAL DEFINITIONS Definition Term Extremity thrombosis Acute symptomatic thrombosis of the venous system of either lower extremity that is not located within the target vessel Iliofemoral venous segment The venous system comprised of the common femoral vein, the external iliac vein, and the common iliac vein (2012 SVS/AVF Guidelines. See Appendix 1). Nonmalignant venous Non-thrombotic or post-thrombotic obstruction of the obstruction iliofemoral venous segment that is not due to direct incursion of the vein by malignancy Venous Obstruction Reduction of the venous lumen diameter \geq 50% when compared to the diameter of the normal vein/RVD immediately peripheral to the obstructed vein as measured by venogram. Total obliteration of the venous lumen Venous Occlusion **PROCEDURAL DEFINITIONS** Definition Term ≥50% reduction of the venous lumen diameter when Binary stenosis (or obstruction) compared to the venous lumen diameter of the normal vein immediately peripheral to the obstructed vein as measured by venogram Lesion success Achievement of ≤50% residual diameter stenosis of the target lesion using any percutaneous method (including the use of non-study devices) Device movement >10mm related to anatomical landmarks or Migration any migration leading to symptoms or requiring therapy Procedural success Technical success without the occurrence of major adverse event between the index procedure and discharge Residual diameter stenosis The greatest degree of stenosis in the target lesion postprocedure, defined by the percent reduction in vessel lumen diameter when compared to the normal vein immediately peripheral to the target lesion as measured by venogram. Stent Embolization Dislodgement of the entire stent, which is carried by the blood flow to a different anatomical site of the vascular system, with no overlap in comparison to the original stent placement

STE-HUM-007P US Clinical Protocol Revision C

Target lesion	The treated segment starting 5 mm peripheral and ending 5 mm centrally to the study device(s)
Target vessel	Native vein containing the target lesion such as the common iliac vein (CIV), external iliac vein (EIV) or common femoral vein (CFV)
Target vessel stenosis	Maximum percentage reduction in target lesion diameter when compared with the diameter of the normal vein/RVD immediately below the lesion as measured by venogram

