- 16. Known hypersensitivity to nickel or titanium
- 17. Contrast agent allergy that cannot be managed adequately with pre-medication
- Intended concurrent thrombolysis or thrombectomy procedure OR intended or planned (within 30 days) adjuvant procedure such as creation of temporary AV fistula, placement of IVC filter, endovenectomy or saphenous vein ablation
- 19. Current or recent (within 30 days) active participation in another drug or device clinical trial (Participation in observational studies is acceptable.)
- 20. Patient judged to be a poor candidate by the primary investigator
- 21. Patients who have had any prior surgical or endovascular intervention of the target vessel Note: Patients who have had catheter-directed or mechanical thrombolysis in the target vessel for DVT at least 3 month (90 days) prior to the VIRTUS index procedure may be included in the trial.
- 8.2.3 Exclusion Criteria Intra-procedural Criteria
 - 22. Patients in whom the lesions cannot be traversed with a guide wire. These patients will not count against the study sample size.
 - 23. Patients where the obstruction extends into the inferior vena cava or below the level of the lesser trochanter. These patients will not count against the study sample size.
 - 24. Patients whose vein diameters are not within limits stated in current Instructions for Use as determined by venogram. These patients will not count against the study sample size.
 - 25. Patients who do not meet the venogram binary stenosis definition above, as determined by the treating physician. These patients will not count against the study sample size.

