15.8 Evaluation of Endpoints

15.8.1 Primary Efficacy Endpoint

The primary efficacy endpoint for this study will be the primary patency rate at 12 months post-intervention. Stented limbs will be assigned the status of *patency failure* if they are known to have a patency failure event:

- Thrombosis including the stented area of the vein
- Re-intervention including the stented area
- Venous imaging study at any time through 12 months showing a restenosis of greater than 50%.

Patients will be assigned the status of *patency success* if their venous imaging study at 12 months showed no greater than 50% restenosis (and no prior study showed greater than 50% restenosis).

STE-HUM-007P US Clinical Protocol Revision C

In the per-protocol (PP) analysis, only patients that meet either of these two criteria will be included. Patients with no imaging study at 12 months and no patency failure event will be ignored in the analysis.

In the worst-case and tipping point analyses, all patients will be included. Patients who were ignored in the PP analysis will be treated as patency failures.

Both the PP and worst-case analyses will test the following hypotheses:

$$\begin{aligned} \mathsf{H}_{0} &: q_{NT} * (p_{NT} - PG_{NT}) + q_{PT} * (p_{PT} - PG_{PT}) \le 0 \\ \mathsf{H}_{A} &: q_{NT} * (p_{NT} - PG_{NT}) + q_{PT} * (p_{PT} - PG_{PT}) > 0, \end{aligned}$$

where p_{NT} and p_{PT} are the observed 12-month patency rates for NT and PT subjects, respectively; PG_{NT} and PG_{PT} are pre-specified fixed performance goals for NT and PT subjects, respectively; and q_{NT} and q_{PT} , both are fixed weights for NT subjects (0.26) and PT subjects (0.74), respectively. The sample weights will not be adjusted based on actual enrollment rates.

The hypothesis test for this endpoint will be tested using a one-sided weighted Z-test at the 0.025 significance level. The test statistic for this hypothesis test is:

$$Z = \frac{q_{NT} * (p_{NT} - PG_{NT}) + q_{PT} * (p_{PT} - PG_{PT})}{\sqrt{q_{NT}^2 * \frac{PG_{NT}(1 - PG_{NT})}{n_{NT}} + q_{PT}^2 * \frac{PG_{PT}(1 - PG_{PT})}{n_{PT}}}$$

where p_{NT} is the proportion of successes in the NT population, PG_{NT} is the performance goal of 85.5% for the NT population, q_{NT} is the predefined weight of 0.266 for the NT population, p_{PT} is the proportion of successes in the PT population, PG_{PT} is the performance goal of 67.9% for the PT population, q_{PT} is the pre-defined weight of 0.74 for the PT population.

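### The safety endpoint counts a pulmonary embolism only if shown on CT, and its DVT component uses an undefined term that may leave some target-vein thrombosis outside both primary endpoints

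*Combined protocol and SAP*

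**What the plan says.** Section 7.2 makes the primary safety endpoint a composite of any MAE within 30 days, adjudicated by the Clinical Events Committee (CEC), and refers to Section 11.1.4 for the list. That section describes the components as "primary safety endpoints occurring within 30 days of the study procedure". Three of them matter here:

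- Embolism: "Clinically significant pulmonary embolism defined as being symptomatic with chest pain, hemoptysis, dyspnea, hypoxia etc... AND be documented on CT". No other means of confirmation is named.
- DVT: "Device or procedure related acute DVT outside of the target vein segment".
- Death: "Device or procedure-related death".

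Section 1 defines two anatomical terms. The *target lesion* is the treated segment, that is, the stent plus 5 mm at each end. The *target vessel* is the native common iliac, external iliac or common femoral vein that contains the lesion. It does not define *target vein segment*.

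Thrombosis of the target vein otherwise belongs to the efficacy endpoint, which is described in three ways. Section 7.1 requires freedom from thrombotic occlusion and does not limit this to the stent. Section 1 describes in-stent thrombosis as occlusion of the stented target vessel. The analysis rule in Section 15.8.1 counts "Thrombosis including the stented area of the vein".

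Sections 15.7.1 and 15.8.2 test freedom from MAE against 0.94 with a one-sided exact binomial test at 0.025. Section 15.7.1 expects an event rate of about 1% and more than 90% power with about 170 patients.

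**The concern.** Embolism and DVT are characteristic harms of a venous stent procedure. In a single-arm trial with a fixed goal, an event that occurs but does not meet the definition raises the observed freedom from MAE, and no control arm shares the bias.

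Two wordings allow this. The first ties embolism to one imaging method, so the score depends on which test the treating hospital chose as well as on whether the embolism occurred. The second draws the DVT boundary with an undefined term, while the efficacy sections draw theirs in different places. An acute thrombosis lying between the two boundaries may fail neither primary endpoint. It would still be recorded as an adverse event, but it would not enter the test against 0.94.

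**Working it through.** **1. The plan's own figure.** Inputs from Sections 15.7.1 and 15.8.2: n = 170, goal 0.94 (event rate 0.06 under the null), one-sided 0.025, expected event rate 0.01. For event rate q and limit c,

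P(X ≤ c) = Σ C(n,x) q^x (1−q)^(n−x), summed over x = 0 to c.

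At q = 0.06 the terms for x = 0 to 4 are 0.00003, 0.00029, 0.00158, 0.00565 and 0.01507. They sum to 0.0226, which is below 0.025. The term for x = 5 is 0.03193 and brings the sum to 0.0545. The test therefore passes with at most 4 events and fails with 5. At q = 0.01, P(X ≤ 4) = 0.971, which agrees with the stated power of more than 90%. With 165 evaluable patients the limit falls to 3 events (p = 0.0095; 4 events give p = 0.0277).

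**2. What undercounting does.** The documents give no rate for embolism confirmed without CT or for thrombosis confined to the unstented target vein, so the hidden share is an assumption. With one event in five hidden, the observed rate is 0.8 times the true rate:

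| True rate | Observed rate | Chance of passing, all counted | Chance of passing, one in five hidden |
|---|---|---|---|
| 1.25% | 0.8 × 1.25% = 1.0% | 93.7% | 97.1% |
| 2.5% | 0.8 × 2.5% = 2.0% | 58.0% | 74.5% |

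If the complete rate were 6%, exactly at the goal, and 0.5 or 1.0 percentage point went uncounted, the chance of passing would rise from 0.0226 to 0.040 or 0.069.

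**3. Embolism.** A symptomatic, non-fatal embolism shown by ventilation-perfusion scan, or by catheter or MR pulmonary angiography, meets the first half of the definition and fails the second. Nothing elsewhere in the documents lets the CEC accept an equivalent test. A fatal embolism judged related to the device or procedure is counted as a death without CT.

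**4. Target-vein thrombosis.** The sections compare as follows for an acute, device- or procedure-related thrombosis within 30 days:

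| Thrombus | MAE if the term means target lesion | MAE if the term means target vessel | Failure under 15.8.1 | Failure under 7.1 |
|---|---|---|---|---|
| Includes the stented area | No | No | Yes | If occlusive |
| Unstented target vein, beyond the 5 mm margin, occlusive | Yes | No | No | Yes, on plain wording |
| Same place, non-occlusive | Yes | No | No | No |
| Confined to a 5 mm margin | No | No | No | If occlusive |

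If the term means target vessel and 15.8.1 governs, the last three rows fail neither primary endpoint. The gap is clearest for the non-occlusive thrombus beyond the margin, which 7.1 does not catch either. The last row shows that equating the term with the target lesion, with no other change, would still leave a strip 5 mm wide at each end.

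**The case against.** Much of the opposing case is sound.

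- **A reader might infer that target-vein thrombosis is in no endpoint at all.** The documents do not support that. If the undefined term means the treated segment, a related DVT beyond the 5 mm margins is already an MAE. An occlusive thrombosis of the vessel is a patency failure on the plain wording of 7.1. A 30-day complication that is not an MAE, needs no hospitalization and does not delay discharge is an ancillary minor outcome under Section 7.4.
- **A reader might infer that the eligibility rules make CT unlikely in some patients.** The trial admits patients with an eGFR down to 30 mL/min (45 in diabetes), and on contrast it excludes only "Contrast agent allergy that cannot be managed adequately with pre-medication". But every treated patient has contrast venography, so these rules select people who can receive contrast. The documents do not show that CT would be avoided.
- **Autopsy-proven embolism is mostly covered**, through related death. The embolism component also has no relatedness condition, which makes it broader in that respect than the DVT component.
- **Events are not hidden from oversight.** Serious adverse events are reported within 24 hours, and the safety board reviews all safety data. Section 4.2 reports no embolism in the published literature, and the plan expects only about 1% for all components together.

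These arguments limit the size of the problem but do not remove it. Reporting to the safety board does not bring an event into the test against 0.94. The alternative readings of the DVT boundary show that the same event can be classified differently by different sections.

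**Conclusion.** The embolism point holds on the plain text: a symptomatic, non-fatal embolism objectively confirmed by a method other than CT is not a primary safety event.

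The DVT point holds conditionally. The term is undefined and Sections 1, 7.1 and 15.8.1 disagree. Only if the term means target vessel and 15.8.1 governs does acute thrombosis confined to the unstented target vein fail neither primary endpoint.

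The direction of any bias is certain and favours the device; its size is unknown. One event can matter, because the limit at 170 patients lies between 4 and 5 events, but that is true of every component and does not show that any event would be missed. A rise from 58% to 75% in the chance of passing should not be read as the expected effect. It assumes a true rate of 2.5%, well above the plan's 1%. Close to the planned rate, the same assumed share moves the chance only from 93.7% to 97.1%. The safety power statement is correct.

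**What to change.** 1. **Embolism component of 11.1.4.** Change the wording to: symptomatic and documented on CT, ventilation-perfusion scan, pulmonary angiography (catheter or MR) or autopsy.
2. **DVT component of 11.1.4.** Define *target vein segment* by the same boundary that 15.8.1 uses for patency failure. One way is to count as an MAE any device- or procedure-related acute DVT that does not include the stented area. The other is to define the term as the target lesion and extend the thrombosis criterion in 15.8.1 to the whole target lesion, including the 5 mm margins. The first leaves the 15.8.1 criterion unchanged; the second widens it.
3. **Reconcile Sections 1, 7.1, 11.1.4 and 15.8.1**, including whether thrombosis must be occlusive, so that each device- or procedure-related acute thrombosis within 30 days falls in one primary endpoint. Put the same wording in the CEC's adjudication rules.

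These are changes of definition, with no added test or visit. The downside is that the reported MAE rate may be slightly less favourable. If fuller counting raised the true rate from 1.0% to 1.25%, power at 170 patients would fall from 97.1% to 93.7%, still above the stated 90%; at 1.5% it would be 88.6%. If the second option in item 2 is chosen, the patency rate may also be slightly lower.

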11.1.5 Adverse Device Effects (ADE)

Adverse event related to the use of an investigational medical device. This includes any event resulting from: insufficiencies or inadequacies in the instructions for use, the deployment, the implantation, the installation, the operation, or any malfunction of the investigational medical device.

11.1.6 Serious Adverse Device Effects (SADE)

ADE that has resulted in any of the consequences and characteristic of a SAE.

STE-HUM-007P US Clinical Protocol Revision C

Confidential

Page 35 of 70

11.1.7 Unanticipated Serious Adverse Device Effects (USADE)

SADE which by its nature, incidence, severity or outcome has not been identified in the current version of the risk analysis report.

11.2 Reporting of Adverse Events

The event is considered to be reported to the Sponsor once the site completes an AE eCRF in electronic data capture (EDC) system.

The information provided for each AE on Adverse Event eCRF must include:

- Description of the event
- Date of event onset
- Date of event outcome
- Date of discovery by site
- Seriousness of the event (e.g., SAE vs. non-SAE)
- Severity of the event
- Relationship of the event to the study procedure, study device
- Actions taken as a result of the event
- Outcome of the event

Every effort should be made to gather as much information as possible regarding reporting serious or unanticipated event within 24 hours. As additional information regarding reporting event becomes available, it should be entered in EDC and source documents should be sent to the Sponsor or Sponsor's designee.

11.3 Relatedness to the Study Procedure, Study Device

Relationship Assignment: Relationship assessment of AEs to the study procedure, study device will be made by the Investigator using the following definitions:

Definitely Related

The clinical event occurs in a plausible time relationship to study procedure/study device and cannot be explained by any concurrent disease or other devices, drugs or chemicals.

Probably Related

The clinical event occurs within a reasonable time sequence to study procedure/study device and the possibilities of factors other than the study procedure/study such as concurrent disease or other devices, drugs or chemicals can be probably excluded.

Possibly Related

The clinical event occurs within a reasonable time sequence to study procedure/study device and there is some evidence to "possibly" suggest a causal relationship. However, the influence of other factors such as underlying disease, concomitant medications, or concurrent treatment may have contributed to the event.

STE-HUM-007P US Clinical Protocol Revision C

Confidential

Page 36 of 70
Not related

The clinical event is completely independent of study procedure/study device and/or evidence exists that the event is definitely related to another etiology.

